5.2.3.1 Prior HCV Therapy

Any HCV therapy the subject received after terminating from the previous AbbVie/Abbott DAA combination study and prior to enrollment in this study must be recorded. Use of any investigational anti-HCV agents or approved DAAs during this period excludes a subject from this study. Subjects who received pegIFN and RBV during this period may be enrolled in the study. These subjects should have complete documentation of pegIFN and RBV treatment history, including start and stop dates, type of response (if known), and reason for discontinuation. Categories on the eCRF will include the following:

- **Null responder:** Subject has documentation that they previously received PegIFN/RBV for at least 10 weeks and failed to achieve a $2 \log_{10}$ IU/mL HCV RNA decrease at Week 12 (Week 10 to Week 16)
- **Partial responder:** Received at least 20 weeks of PegIFN/RBV for the treatment of HCV and achieved $\geq 2 \log_{10}$ reduction in HCV RNA at Week 12 (Weeks 10 – 16), but failed to achieve HCV RNA undetectable at the end of treatment
- **Relapser:** Received at least 36 weeks of PegIFN/RBV for the treatment of HCV and was undetectable at the end of treatment, but HCV RNA was detectable within 52 weeks of treatment follow-up
- **Not documented/Other**

5.2.3.2 Prohibited Therapy

In addition to the medications listed above in [Table 4](#), use of known strong inducers of CYP3A is prohibited within 2 weeks or 10 half-lives, whichever is longer, prior to the initial dose of study through the first 2 weeks after the subject has completed DAA therapy.

Use of any medications contraindicated with pegIFN or RBV is prohibited within 2 weeks prior to the initial dose of study drug through the first 2 weeks after the subject has completed Substudy 2.

Prior to enrollment, subjects should agree to practice two effective methods of birth control while receiving study drugs starting with Study Day 1 and for 7 months after stopping study drug or as directed by the local ribavirin label. Subjects using systemic estrogen-containing contraceptive therapy (including estrogen-containing oral contraceptives) have a higher risk for elevated ALT levels. Subjects using these medications must discontinue them at least 2 weeks prior to study drug administration or 10 half-lives (if known), whichever is longer. Subjects may replace the systemic estrogen-containing contraceptive with a progestin-only hormonal contraceptive method. Estrogen-containing contraceptives may be resumed 2 weeks after the last dose of DAAs.

Refer to the pegIFN, RBV and ritonavir labeling for a list of prohibited medications. HCV medications other than those specified in the protocol will not be allowed during the Treatment Period of the study.

Use of hematopoietic growth factors is not permitted during this study without the approval of the AbbVie Study Designated Physician. Management of hematologic growth factor therapy is the responsibility of the investigator; growth factors will not be provided by the Sponsor, and the Sponsor will not reimburse for the expense of growth factors or their use.

Investigators should refer to the package inserts for erythropoiesis stimulating agents for additional information regarding their use.

5.2.3.3 Post-Treatment Therapy

No further treatment is planned after subjects have ended their participation in the study. This study is intended to offer intensified therapy with two investigational drugs plus pegIFN and RBV for subjects who have failed treatment for HCV infection in a previous AbbVie/Abbott study. Some safety assessments, measurements of HCV RNA (HCV viral levels) and monitoring for viral resistance are performed for 48 weeks following the last dose of study treatment.

If a subject meets virologic failure criteria in this study or relapses in the post-treatment follow-up period (Substudy 3), the investigator should treat the subject according to his/her best clinical judgment.

5.3 Efficacy, Pharmacokinetic, Pharmacogenetic, and Safety Assessments/Variables

5.3.1 Efficacy and Safety Measurements Assessed and Flow Chart

Study procedures are summarized in [Table 5](#) and [Table 6](#) (for cirrhotic subjects).

Table 5. Study Activities

| Activity | Pre-SCR | SCR | Substudy 1 Treatment Intensification (TI) Period | | | | | | | | | | Substudy 2-PegIFN/RBV Alone (PR) | | | | | |
|---|---------|----------------|--|---------|---------|---------|---------|----------|----------|----------|----------------------------|---------|----------------------------------|---------|----------|-----------------------|-----------------------|---------------------------------|
| | | | TI Day 1 ^b | TI Wk 1 | TI Wk 2 | TI Wk 4 | TI Wk 8 | TI Wk 12 | TI Wk 16 | TI Wk 20 | TI Wk 24/ D/C ^c | PR Wk 2 | PR Wk 4 | PR Wk 8 | PR Wk 12 | PR Wk 24 ^d | PR Wk 36 ^d | PR Final/ PR D/C ^{d,e} |
| Informed Consent ^a | X | | | | | | | | | | | | | | | | | |
| Population Sequencing Assessment | X | | | | | | | | | | | | | | | | | |
| Provide pegIFN/RBV Information and Medication Guides ^f | | X | | | | | | | | | | | | | | | | |
| Medical History ^g | | X | | | | | | | | | | | | | | | | |
| Adverse Event Assessment | | | X | X | X | X | X | X | X | X | X | X | X | X | X | X | X | X |
| Concomitant Medication Assessment | | X | X | X | X | X | X | X | X | X | X | X | X | X | X | X | X | X |
| Physical Examination | | X ⁱ | | | | | | | | | | | | | | | | X |
| Vital Signs and Weight | | X | X | X | X | X | X | X | X | X | X | X | X | X | X | X | X | X |
| 12-Lead ECG | | X | | | | | | | | | | | | | | | | X |
| Pregnancy Test ^j (Females) | | X(u) | | | | | | | | | | | | | | | | X(u) |
| Serum (s) Urine (u) | | (s) | | | | | | | | | | | | | | | | X(u) |
| FSH (all females) | | X | | | | | | | | | | | | | | | | |

Table 5. Study Activities (Continued)

| Activity | Pre-SCR | SCR | Substudy 1 Treatment Intensification (TI) Period | | | | | | | | | | Substudy 2-PegIFN/RBV Alone (PR) | | | | | |
|--|---------|-----|--|---------|---------|---------|---------|----------|----------|----------|-------------------------------|---------|----------------------------------|---------|----------|-----------------------|-----------------------|------------------------------------|
| | | | TI Day 1 ^a | TI Wk 1 | TI Wk 2 | TI Wk 4 | TI Wk 8 | TI Wk 12 | TI Wk 16 | TI Wk 20 | TI Wk 24/ D/C ^c | PR Wk 2 | PR Wk 4 | PR Wk 8 | PR Wk 12 | PR Wk 24 ^d | PR Wk 36 ^d | PR Final/ PR D/C ^{d,e} |
| HBsAg, Anti HIV Ab | | X | | | | | | | | | | | | | | | | |
| Drug/Alcohol Screen | | X | | | | | | | | | | | | | | | | |
| HCV Genotype | | X | | | | | | | | | | | | | | | | |
| Clinical Laboratory Tests | | X | X | X | X | X | X | X | X | X | X | X | X | X | X | X | X | X |
| Total Insulin | | | | | | | | | | | | | | | | | | |
| TSH | | X | | | | | | | | | | | | | | | | |
| BDI-II Depression Scale | | X | | | | | | | | | | | | | | | | |
| Study Drugs Dispensed/ Drug Accountability ^k | | | | | | | | | | | | | | | | | | |
| Dispense MEMS Cap ^l | | | | | | | | | | | | | | | | | | |
| Download MEMS ^l | | | | | | | | | | | | | | | | | | |
| Collect MEMS Cap ^{l,m} | | | | | | | | | | | | | | | | | | |

Table 5. Study Activities (Continued)

| Activity | Pre-SCR | SCR | Substudy 1 Treatment Intensification (TI) Period | | | | | | | | | | Substudy 2-PegIFN/RBV Alone (PR) | | | | | | |
|--|---------|-----|--|---------|---------|---------|---------|----------|----------|----------|----------------------------|---------|----------------------------------|---------|---------|----------|-----------------------|-----------------------|------------------------------|
| | | | TI Day 1 ^a | TI Wk 1 | TI Wk 2 | TI Wk 4 | TI Wk 8 | TI Wk 12 | TI Wk 16 | TI Wk 20 | TI Wk 24/ ^c D/C | TI Wk 2 | PR Wk 2 | PR Wk 4 | PR Wk 8 | PR Wk 12 | PR Wk 24 ^d | PR Wk 36 ^d | PR Final/ ^{d,e} D/C |
| HCV RNA Sample | X | X | X | X | X | X | X | X | X | X | X | X | X | X | X | X | X | X | X |
| HCV Resistance Testing Sample | X | | X | X | X | X | X | X | X | X | X | X | X | X | X | X | X | X | X |
| DAA/ritonavir, PegIFN/RBV Assay (PK) Sample ⁿ | | | X | X | X | X | X | X | X | X | X | X | X | X | X | X | X | X | X |
| IP-10 Testing | X | | | | | | | | | | | | | | | | | | X |

SCR = Screening; D/C = Premature discontinuation; Wk = Week

- Prior to performing any study-specific procedures.
- Activities to be performed prior to first dose of any study drug.
- Subjects who prematurely discontinue from the DAA study drug treatment in Substudy 1 should return for a TI Week 24/TI Discontinuation Visit. These subjects will continue on to Substudy 2 if the investigator feels it is appropriate or proceed to Substudy 3 if it is not appropriate to continue on Substudy 2.
- These visits are only needed for subjects who did not complete 24 weeks of pegIFN/RBV in Substudy 1 such that the subject completes a total of 48 weeks of pegIFN/RBV across Substudy 1 and Substudy 2.
- Subjects who prematurely discontinue from the pegIFN/RBV study drug treatment in Substudy 2 should return for a PR Final/PR Discontinuation Visit. These subjects will continue on to Substudy 3.

Table 5. Study Activities (Continued)

- f. Where applicable/locally available.
- g. The subject's medical history will be updated at the Screening Visit with any relevant information that was not collected in the previous AbbVie/Abbott DAA combination study and any new medical history that occurred between the end of the previous AbbVie/Abbott DAA combination study and this study. The subject's medical history will also be updated if needed for the period between the Screening Visit and the TI Day 1 Visit.
- h. Only concomitant medications related to HCV treatment and/or medications prescribed in association with a serious adverse event will be collected during Substudy 2.
- i. Height will be measured at Screening only. Will include a thorough eye exam to confirm that the subject is an appropriate candidate for pegIFN therapy.
- j. Urine pregnancy testing is not required after the TI Day 1 Visit for female subjects with a documented prior hysterectomy or bilateral oophorectomy or bilateral tubal ligation or those confirmed to be postmenopausal. Urine pregnancy tests must be conducted monthly during treatment in Substudy 1 and Substudy 2 (per local RBV label) for women of childbearing potential. Subjects may come to the clinic for an unscheduled visit for pregnancy testing at PR Study Weeks 16 and 20 and PR Weeks 28, 32, 40 and 44 if needed or perform the tests at home with test kits provided by the site. Sites may substitute serum pregnancy testing for urine pregnancy testing only if required per local regulations.
- k. Refer to Section 5.5.1 for additional information on treatments administered and Section 5.5.8 for additional information on drug accountability. Drug Accountability is not assessed at TI Day 1.
- l. Collected from subjects participating in study under original protocol and Amendments 1 – 9.
- m. MEMS cap is collected at any point upon completion of Substudy 1.
- n. A total of two pharmacokinetic samples will be drawn at each time-point, one plasma and one serum. The site will contact the subject approximately 2 days prior to the scheduled PK blood collection date to review the importance of proper study drug administration.

Table 6. Additional Study Activities for Cirrhotic Subjects Only

| Activity | Pre-SCR | SCR | Substudy 1 Treatment Intensification (TI) Period | | | | | | | | | | Substudy 2-PegIFN/RBV Alone (PR) | | | | | | |
|--|---------|----------------|--|---------|---------|---------|---------|----------|----------|----------|---------------------|---------|----------------------------------|---------|---------|----------|-----------------------|-----------------------|------------------------------------|
| | | | Substudy 1 Treatment Intensification (TI) Period | | | | | | | | | | Treatment Period | | | | | | |
| | | | TI Day 1 | TI Wk 1 | TI Wk 2 | TI Wk 4 | TI Wk 8 | TI Wk 12 | TI Wk 16 | TI Wk 20 | TI Wk 24/ TI D/C | TI Wk 2 | PR Wk 2 | PR Wk 4 | PR Wk 8 | PR Wk 12 | PR Wk 24 ^d | PR Wk 36 ^d | PR Final/ PR D/C ^{d,e} |
| Child-Pugh Score | | X | | | | | | | | X | | | | | | | | | X |
| Clinical Assessment of Hepatic Decompensation | | | X ^a | | | | | | | | | | | | | | | | |
| HCC Screening: Liver Ultrasound and Alpha Fetoprotein ^c | | X ^b | | | | | | | | | | | | | | X | | | X |

- a. Clinical assessment of hepatic decompensation based on physical exam on TI Day 1 prior to dosing.
- b. Subjects with a historical negative Liver Ultrasound, CT or MRI (within 3 months prior to screening) are not required to have a Screening Ultrasound performed.
- c. If additional liver ultrasound testing is required it should be completed as an unscheduled visit. A positive ultrasound result suspicious for HCC will be confirmed with CT scan or MRI.
- d. These visits are only needed for subjects who did not complete 24 weeks of pegIFN/RBV in Substudy 1 such that the subject completes a total of 48 weeks of pegIFN/RBV across Substudy 1 and Substudy 2.
- e. Subjects who prematurely discontinue from the pegIFN/RBV study drug treatment in Substudy 2 should return for a PR Final/PR Discontinuation Visit. These subjects will continue on to Substudy 3.

Table 7. Study Activities – Substudy 3 Post-Treatment

| Activity | Substudy 3 Post-Treatment (PT) Period | | | | | | | |
|---|---------------------------------------|---------|---------|----------|----------|----------|---------------------|--|
| | PT Wk 2 | PT Wk 4 | PT Wk 8 | PT Wk 12 | PT Wk 24 | PT Wk 36 | PT Wk 48/ PT D/C | |
| Adverse Event Assessment ^a | X | X | X | X | X | X | X | |
| Concomitant Medication Assessment ^b | X | X | X | X | X | X | X | |
| Vital Signs and Weight | X | X | X | X | X | X | X | |
| Pregnancy Test (Females) Urine (u) ^c | X | X | X | X | X | | | |
| Clinical Laboratory Tests | X | X | | | | | X ^d | |
| IP-10 | | | | | X | | X ^d | |
| HCV RNA Sample | X | X | X | X | X | X | X | |
| HCV Resistance Testing | X | X | X | X | X | X | X | |
| Archive Plasma Sample | X | X | | | | | X | |

PT = Post-treatment; Wk = week; D/C = discontinuation

- AEs will be collected for only 30 days following last dose of study drugs. SAE's will be collected during the entire Substudy 3 period.
- Only concomitant medications related to HCV treatment and/or medications prescribed in association with a serious adverse event will be collected during Substudy 3.
- Post-treatment pregnancy testing is to be completed at the visits outlined in Table 7. Additional pregnancy testing (urine and/or serum) during the Post-treatment Period, e.g., at PT Week 16, PT Week 20, PT Week 28 or at other time points should be completed according to the local RBV label and/or local treatment guidelines for RBV or local legal requirements. Additional pregnancy testing (urine and/or serum) done outside of the visits specified in Table 7 should be completed using the unscheduled test kit or the subject can perform the tests at home with test kits provided by the site.
- Sample to be drawn only if conducting a Discontinuation Visit.

Table 8. Additional Study Activities for Cirrhotic Subjects Only – Substudy 3 Post-Treatment

| Activity | Substudy 3 Post-Treatment (PT) Period | | | | | | | |
|--|---------------------------------------|---------|---------|----------|----------|----------|---------------------|--|
| | PT Wk 2 | PT Wk 4 | PT Wk 8 | PT Wk 12 | PT Wk 24 | PT Wk 36 | PT Wk 48/ PT D/C | |
| Clinical Laboratory Tests | X | X | | | X | | X | |
| Child-Pugh Score | | | | X | | | | |
| HCC Screening: Liver Ultrasound and Alpha Fetoprotein ^a | | | | | X | | X | |

a. If additional liver ultrasound testing is required it should be completed as an unscheduled visit. An ultrasound result suspicious for HCC will be confirmed with CT scan or MRI

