Subjects who complete TI treatment will continue on to Substudy 2, the PR Treatment Period, for continued dosing of pegIFN and RBV. Subjects who prematurely discontinue TI treatment may also continue on to Substudy 2, unless the investigator feels it is not appropriate to continue pegIFN and RBV either due to toxicity or to lack of virologic response. Substudy 2 will begin the day after the last dose of DAA. Substudy 2 is designed to allow completion of pegIFN + RBV treatment for a total duration of 48 weeks across Substudies 1 and 2 and to monitor HCV RNA levels and emergence of any ABT-450 and ABT-267 resistance-associated variants.

For subjects who complete Substudy 1, an additional 24 weeks of pegIFN and RBV will be administered in Substudy 2. Subjects who complete 24 weeks of treatment in Substudy 2 should undergo the procedures listed in the PR Final/PR Discontinuation Visit in [Table 5](#) (and [Table 6](#) for cirrhotic subjects), not the PR Week 24 visit and then continue on to Substudy 3.

Subjects who receive less than 24 weeks of TI treatment in Substudy 1 may receive pegIFN and RBV in Substudy 2 at the discretion of the investigator, up to a total of 48 weeks across Substudies 1 and 2. All subjects will continue to return to the site on an outpatient basis for the PR Treatment study procedures identified in [Table 5](#) (and [Table 6](#) for cirrhotic subjects). For those subjects who do not complete 24 weeks of TI treatment in Substudy 1, additional study visits as indicated in [Table 5](#) (and [Table 6](#) for cirrhotic subjects) should be performed if required to complete a total of 48 weeks across Substudies 1 and 2. These additional visits are PR Week 24, PR Week 36 and PR

Final/PR Discontinuation Visit (which may be out to 48 weeks or earlier). All subjects should complete the PR Final/PR Discontinuation Visit procedures at that subject's final visit in Substudy 2. In some cases this final visit may fall in between study visits listed in [Table 5](#). Sites should ensure that subjects adhere to the study visits listed in [Table 5](#) (and [Table 6](#) for cirrhotic subjects). Subjects who cannot complete their study visit per the visit schedule should ensure they do not run out of study drug prior to their next study visit. Compliance is critical to ensure adequate drug exposure.

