**Relapse12** = confirmed HCV RNA  $\geq$  LLOQ between Final Treatment Visit and 12 weeks after last actual dose of study drug (up to and including SVR12 assessment time point) for a subject with HCV RNA  $<$  LLOQ at the Final Treatment Visit who completes treatment. Completion of treatment is defined as DAA duration  $\geq 161$  days and pegIFN/RBV duration  $\geq 252$  days.

**Relapse24** = confirmed HCV RNA  $\geq$  LLOQ within the SVR24 window for a subject who achieved SVR12 and has HCV RNA data available in the SVR24 window.

**Relapseoverall** = confirmed HCV RNA  $\geq$  LLOQ between Final Treatment Visit and up to and including the last HCV RNA measurement collected in the PT Period for a subject with HCV RNA  $<$  LLOQ at Final Treatment Visit who completes treatment. Completion of treatment is defined as DAA duration  $\geq$  161 days and pegIFN/RBV duration  $\geq$  252 days.

**Relapselate** = confirmed HCV RNA  $\geq$  LLOQ at any time after the SVR24 assessment time point for a subject who achieved SVR24 and has post-SVR24 HCV RNA data available.

If the last available post-treatment value is  $\geq$  LLOQ, then the subject will be considered a relapse (i.e., will not require confirmation). Relapse analyses will exclude subjects who do not have any post-treatment HCV RNA values.

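### Footnotes d and e in protocol Tables 5 and 6, read literally, give no PR Final visit to subjects who complete both substudies, while Section 5.1.3 requires one; the end-of-treatment HCV RNA sample depends on which text a site follows

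*Protocol*

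**What the plan says.** **Schedule tables (protocol Section 5.3.1, Tables 5 and 6).** Three Substudy 2 columns carry footnote d: PR Week 24, PR Week 36 and PR Final/PR D/C. The footnote opens "These visits are only needed for subjects who did not complete 24 weeks of pegIFN/RBV in Substudy 1 such that the subject completes" and goes on to the 48-week total of pegIFN/RBV over the two substudies. The PR Final/PR D/C column also carries footnote e: "Subjects who prematurely discontinue from the pegIFN/RBV study drug treatment in Substudy 2 should return for a PR Final/PR Discontinuation Visit". Both footnotes have the same wording in the two tables.

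**Text (protocol Section 5.1.3, Substudy 2).** One sentence deals with completers. It opens "Subjects who complete 24 weeks of treatment in Substudy 2 should undergo the procedures listed in the PR Final/PR Discontinuation Visit in" and points to Tables 5 and 6; its close, on the visit that is dropped, reads "not the PR Week 24 visit and then continue on to Substudy 3". Later in the section: "All subjects should complete the PR Final/PR Discontinuation Visit procedures at that subject's final visit in Substudy 2". The section also names PR Final, with PR Week 24 and PR Week 36, among the additional visits for subjects who had less than 24 weeks of TI treatment, and it tells sites to keep to the visits in Tables 5 and 6.

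**SAP.** Table 2 has a similar restriction (note a), but on the Week 36 and Week 48 rows only. Its note b defines the Final Treatment Visit for all subjects. Section 6.1 takes the Final Treatment Visit value as the last non-missing measurement after Study Day 1 and up to Study Drug End Day 2. The Relapse-overall definition in Section 10.1 applies to subjects with HCV RNA < "LLOQ at Final Treatment Visit who completes treatment"; Relapse12 has the same condition.

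**The concern.** PR Final is the only scheduled visit at the end of pegIFN/RBV for a subject on the standard 24 + 24 week course. The tables and the text give opposite answers on whether that subject has it. Section 5.1.3 does not simply override the tables, because it also sends sites to them and itself lists PR Final with the additional visits.

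At stake at a site that works from the footnotes are the end-of-treatment HCV RNA sample and the other assessments marked in that column: physical examination, ECG, laboratory tests, PK and IP-10, and Child-Pugh score and HCC screening in cirrhotic subjects. The missing HCV RNA sample would not show as missing in the analysis, because the SAP rule falls back on the previous on-treatment value however old it is.

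**Working it through.** No sample size or error rate bears on this point. The check sets the texts side by side and counts visits.

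**1. Who has PR Final under each text**

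| Subject | Footnotes d and e | Section 5.1.3 |
|---|---|---|
| Under 24 weeks of pegIFN/RBV in Substudy 1, continues in Substudy 2 | Yes (d) | Yes |
| Completes Substudy 1, stops Substudy 2 early | Yes (e) | Yes |
| Completes both substudies | **No** | **Yes, instead of PR Week 24** |
| Goes from Substudy 1 directly to Substudy 3 | No (TI D/C visit) | No (TI D/C visit) |

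The texts differ only in the third row.

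**2. Treatment duration.** 24 weeks (Substudy 1) + 24 weeks (Substudy 2) = 48 weeks, which agrees with the protocol's own total.

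**3. On-treatment HCV RNA samples after Day 1 in a completer (Table 5)**

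- Substudy 1: TI Weeks 1, 2, 4, 8, 12, 16, 20, 24 = 8 samples.
- Substudy 2, not restricted by footnote d: PR Weeks 2, 4, 8, 12 = 4 samples.
- Footnotes read literally: 8 + 4 = **12**; the last at study Week 24 + 12 = **36**.
- Section 5.1.3: 8 + 4 + 1 = **13**; the last at study Week **48**.

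**4. Time not covered**

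- Last on-treatment sample to end of treatment, footnotes: 48 - 36 = 12 weeks, and 12/48 = **25%** of treatment. Section 5.1.3: 0 weeks.
- PR Week 12 to the next sample of any kind: 12 weeks under Section 5.1.3 (to PR Final), and 12 + 2 = 14 weeks under the footnotes (to PT Week 2, Table 7). The interval lengthens by 2 weeks; what is lost is the one sample at its on-treatment end.

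**5. What the SAP does without PR Final**

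- PT Week 2 cannot stand in. Its nominal Study Drug End Day is 14 and its window is 3 to 21 (SAP Table 3); the cut-off for the Final Treatment Visit value is Day 2.
- The PR Week 12 value therefore becomes the Final Treatment Visit value. The rule has no lower limit on timing, so no imputation or failure rule is triggered.

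**6. How one subject can change category.** Take a completer who is < LLOQ at PR Week 12 and quantifiable at the end of treatment and at PT Weeks 2 and 4.

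- With PR Final: SAP Section 10.1 lets the final treatment measurement and the next post-treatment measurement confirm each other. The subject is a breakthrough, hence an on-treatment virologic failure, and not a Final Treatment Visit responder.
- Without PR Final: the Final Treatment Visit value is the < LLOQ result from Week 36. The subject counts as a Final Treatment Visit responder and, with two consecutive quantifiable post-treatment values, as Relapse12.
- Per such subject, with f on-treatment failures and t Final Treatment Visit responders among N, and r relapses among m evaluable completers: f/N becomes (f - 1)/N, t/N becomes (t + 1)/N, and r/m becomes (r + 1)/(m + 1). At N = 35, the planned maximum, 1/35 = 2.9 percentage points.

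**7. What does not move**

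- SVR12 and SVR24 use post-treatment samples from Table 7, and eRVR uses TI Weeks 4 to 12.
- The mITT-GT-VF analysis excludes only non-virologic failures among genotype 1 subjects. The subject in step 6 is a virologic failure under either label.

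**8. A cross-check that does not settle it.** Section 5.3.2.1 plans about 30 PK samples per subject, two per time point. Counting every Substudy 2 column gives 2 x (8 + 7) = 30. A completer has 2 x 13 = 26 under Section 5.1.3 and 2 x 12 = 24 under the footnotes, so the planned figure matches neither reading.

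**The case against.** The strongest reply is that the protocol answers the question for this very subject. Two sentences of Section 5.1.3 call for PR Final, one addressed to completers and one to all subjects, and the first names the Table 5 column to use. The SAP agrees: the Final Treatment Visit is defined for all subjects, and Section 11.3.1 lists IP-10 at PR Final/PR D/C without restriction. The loss needs a site to prefer a footnote to that text, and neither document shows that any site did. This stands, and it makes the consequence conditional.

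The analytic reach is also limited. The affected endpoints are additional, descriptive ones in a single-arm study without comparisons. Laboratory tests and vital signs are taken again at PT Week 2. The SAP's laboratory shift, PCS and toxicity-grade summaries stop at DAA Study Drug End Day 2, 24 weeks before this visit in a completer, and the SAP safety section specifies no ECG analysis. This stands too.

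Three stronger readings are tempting and not supported:

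- A reader might infer that all completers lack an end-of-treatment HCV RNA result. That would require every site to follow the footnotes over Section 5.1.3.
- A reader might infer that the primary result is at risk. SVR12 does not use this visit.
- A reader might put the gap at 14/48 = 29%. That sets two off-treatment weeks against a 48-week treatment period, and 12 of the 14 weeks are the interval already intended between PR Week 12 and PR Final.

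The objection does not remove the contradiction. The superscripts stand on the column in both tables, and Section 5.1.3 tells sites to keep to those tables.

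**Conclusion.** The documents contradict each other on whether a subject who completes both substudies has a PR Final visit. At a site that follows the footnotes, each such subject loses one of 13 on-treatment HCV RNA samples. The last is then at study Week 36, 25% of the treatment course before its end, and the other assessments in that column are lost with it. The SAP would use the earlier value without any flag. Final Treatment Visit Response could be inflated and a late breakthrough counted as relapse, at 2.9 percentage points of a 35-subject cohort for each subject affected.

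This rests on two conditions: that a site applies the footnotes literally, and that a subject who is < LLOQ at PR Week 12 becomes quantifiable by the end of treatment. The documents give no frequency for either, so the number of subjects affected cannot be estimated. SVR12, SVR24 and eRVR are unaffected, and there is no effect where Section 5.1.3 is followed. The point is an internal inconsistency worth correcting, because a sample not drawn cannot be recovered. It is not a flaw in the primary analysis.

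**What to change.** Reconcile three places and tell sites which reading applies:

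- footnote d as attached to the PR Final/PR D/C column of Tables 5 and 6, for example by reviewing whether superscript d belongs on that column;
- Section 5.1.3, both its statements on completers and all subjects and its sentence on additional visits, keeping the timing statement there for subjects with less than 24 weeks of TI treatment;
- SAP Table 2, whose notes a and b should match the outcome.

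The cost is at most one superscript in each of two tables, one sentence and a clarification letter to sites. If sampling has already ended, the study report can list the study day of each completer's Final Treatment Visit HCV RNA value. This shows whether any came from PR Week 12 and needs no new data.
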